Summary Table of Study Protocol

Title	Post-marketing Surveillance Study for Sotorasib in South Korea	
Protocol Version Identifier	2020009	
Date of Last Version of the Protocol	02 August 2022	
EU Post Authorization Study (PAS) Register No	NA	
Active Substance	Sotorasib	
Medicinal Product	Sotorasib tablet 120 mg (AMG 510, LUMAKRAS)	
Device	NA	
Product Reference	NA	
Procedure Number	NA	
Joint PASS	Yes	
Research Question and Objectives	The primary objective is to describe safety of sotorasib in post-marketing clinical practice within the approved indication by estimating the incidence of adverse events, serious adverse events, adverse drug reactions, serious adverse drug reactions, unexpected adverse events, unexpected serious adverse events, unexpected adverse drug reactions, unexpected serious adverse drug reactions, leading to discontinuation of sotorasib, and fatal events; as required by the Ministry of Food and Drug Safety (MFDS). The secondary objective is to describe effectiveness of sotorasib in clinical practice within the approved indication by estimating overall response rate (ORR) and clinical outcome measure by the Investigator.	
Country of Study	South Korea	
Author	PPD	

Marketing Authorization Holder

Marketing authorization holders	Amgen Korea Limited [name] [contact]
MAH Contact	NA

Confidentiality Notice

This document contains confidential information of Amgen Inc.

This document must not be disclosed to anyone other than the site study staff and members of the Institutional Review Board/Independent Ethics Committee/Institutional Scientific Review Board or equivalent, as applicable.

The information in this document cannot be used for any purpose other than the evaluation or conduct of the research without the prior written consent of Amgen Inc.

If you have questions regarding how this document may be used or shared, call the Amgen Medical Information number: Amgen's general number in the US ([name]); in South Korea, it is [name].

Investigator's Agreement

I have read the attached protocol entitled "Post-marketing Surveillance Study for Sotorasib in South Korea," dated 02 August 2022, and agree to abide by all provisions set forth therein.

I agree to ensure that the confidential information contained in this document will not be used for any purpose other than the evaluation or conduct of the clinical investigation without the prior written consent of Amgen Inc.

Signature	
Name of Investigator:	
Title:	
Name of Hospital/Site:	
Address/City/State/Country:	

Date (DD Month YYYY)

Phone Number: Email:

[figure not shown]
[figure not shown]

Figure 1. Study Design Schema

EOS = end of study

Data source - Study data will be collected from the medical records of enrolled patients.

Patient-level characteristics collected:

- demographics, physical measurements, and smoking status (subject number, age, sex, height, weight, smoking history, allergic history, pregnancy, or lactation status)
- clinical and tumor characteristics (date of initial diagnosis, clinical stage, histology, comorbidities [including hepatic impairment and renal impairment], Eastern Cooperative Oncology Group [ECOG] performance score)
- treatment history (prior systemic treatment received in the advanced disease setting, dose, unit and frequency, start and stop dates)
- sotorasib treatment (indication, dose, start date, end date, frequency of sotorasib administration)
- prior and concomitant medications

Investigator Site Information:

• site name, specialty, investigator name, contract date

Safety:

- adverse events
- serious adverse events
- adverse drug reactions
- serious adverse drug reactions
- unexpected adverse events
- unexpected serious adverse events
- unexpected adverse drug reactions
- unexpected serious adverse drug reactions
- adverse events leading to sotorasib discontinuation
- fatal events
- other safety findings
- spontaneously reported product complaints

Clinical outcome:

- Overall Response Rate (ORR)
- clinical outcome measure by the Investigator

1. Table of Contents

Sun	nmary ⁻	Table of S	tudy Protoco	l lo	1
1.	Table	e of Conte	nts		5
2.	List of Abbreviations			9	
3.	Resp	onsible P	arties		9
4.	Abstr	act			10
5.	Amer	ndments a	and Updates		13
6.					
0.	6.1		•	apeutic Area	
	6.2				
	6.3			ity Considerations	
	6.4		-	(Estimation or Hypothesis)	
7.	Rese	arch Que	stion and Ob	ojectives	15
	7.1	Primary	/		15
	7.2	Second	lary		15
8.	Rese	arch Meth	nods		15
	8.1	Study E	Design		15
	8.2	Setting	and Study P	Population	20
		8.2.1	Study Per	riod	20
		8.2.2	Selection	and Number of Sites	20
		8.2.3	Subject P	Professional Eligibility	20
			8.2.3.1	Inclusion Criteria	20
			8.2.3.2	Exclusion Criteria	20

Appendix A.	List of Stand-alone Documents	40
Appendix B.	ENCePP Checklist for Study Protocols	41
Appendix C.	Sample Safety Reporting Form(s)	48
Appendix D.	Additional Safety Reporting Information	50
Appendix E.	Pregnancy and Lactation Notification Forms	51

Abbreviation or Term	Definition/Explanation
BOR	Best Overall Response
CR	complete response
CTCAE	Common Terminology Criteria for Adverse Events
ECOG	Eastern Cooperative Oncology Group
eCRF	electronic case report form
EOS	end of study
ERK	extracellular signal regulated kinase
ICF	informed consent form
IEC	independent ethics committee
IRB	institutional review board
KRAS	Kirsten rat sarcoma viral oncogene homolog (protein)
KRAS	Kirsten rat sarcoma viral oncogene homolog (DNA)
KRAS p.G12C	KRAS DNA with a mutation resulting in a G12C mutation at the protein level
KRAS ^{G12C}	KRAS protein with a G12C mutation at the protein level
MedDRA	Medical Dictionary for Regulatory Activities
MFDS	Ministry of Food and Drug Safety
NA	not applicable
NE	not evaluable disease
NSCLC	non-small cell lung cancer
ORR	Overall Response Rate
PAS	post authorization study
PD	progressive disease
PR	partial response
PT	Preferred Term
RAF	RAF proto-oncogene serine/threonine-protein kinase
RECIST	response evaluation criteria in solid tumors
RMP	Risk Management Plan
SD	stable disease
SOC	System Organ Class

2. List of Abbreviations

3. Responsible Parties

The sponsor of the study is Amgen Korea Limited. The list of investigators will be determined by which sites have access to sotorasib. Once the list is compiled, the sponsor or delegate may provide it upon request.

4. Abstract

• Study Title

Post-marketing Surveillance Study for Sotorasib in South Korea

• Study Background and Rationale

Sotorasib is the first Kirsten rat sarcoma viral oncogene homolog protein (KRAS) with a G12C mutation (KRAS^{G12C}) inhibitor to treat *KRAS p.G12C* positive cancer. Sotorasib has clinical trial data (Li et al, 2021; Hong et al, 2020) and has been approved by Ministry of Food and Drug Safety (MFDS). In South Korea, approximately 2% to 4% of patients with non-small cell lung cancer (NSCLC) harbor the *KRAS p.G12C* mutation, and each year approximately 450 to 900 new patients in the South Korea are diagnosed with *KRAS p.G12C*-mutated NSCLC (Korea National Cancer Information Center, 2020; Park et al, 2017; Shin et al, 2017; Sun et al, 2013).

In South Korea, it is mandatory to conduct active pharmacovigilance surveillance as a part of the Risk Management Plan (RMP) to investigate post-marketing safety and effectiveness in patients treated with approved orphan drugs. To comply with this Korean MFDS regulation, Amgen Limited Korea will conduct a post-marketing surveillance study to evaluate the safety and effectiveness of sotorasib in routine clinical practice.

• Study Feasibility and Futility Considerations

Not applicable

Objectives	Endpoints		
Primary			
describe safety of sotorasib in post-	incidence of adverse events		
marketing clinical practice within the approved indication	incidence of serious adverse events		
	incidence of adverse drug reactions		
	 incidence of serious adverse drug reactions 		
	 incidence of unexpected adverse events 		
	 incidence of unexpected serious adverse events 		
	 incidence of unexpected adverse drug reactions 		
	 incidence of unexpected serious adverse drug reactions 		
	 incidence of adverse events leading to sotorasib discontinuation 		
	incidence of fatal events		

• Research Question and Objectives

Secondary

 describe effectiveness of sotorasib in clinical practice within the approved indication 	 Overall Response Rate (ORR) clinical outcome measure by the
Exploratory	Investigator

.

NA

• NA

Hypothesis/Estimation

No hypothesis will be tested. This study will describe the incidence of adverse events, serious adverse events, adverse drug reactions, serious adverse drug reactions, unexpected adverse events, unexpected serious adverse events, unexpected adverse drug reactions, unexpected serious adverse drug reactions, adverse events leading to sotorasib discontinuation, and fatal events; overall response rate (ORR) after initiation of sotorasib in South Korea.

• Study Design/Type

This is an observational multicenter study in patients who are prescribed sotorasib within the approved indication in a post-marketing setting in South Korea.

• Study Population or Data Resource

Study enrollment will be offered to patients meeting the eligibility criteria at participating medical sites in South Korea. Enrollment will start (estimated fall of 2022) after launch of sotorasib in South Korea and is planned to end 2 years later if enrollment targets are met. A discussion with MFDS will be completed to determine if an extension is required. Patients will be enrolled at participating sites and will be followed for up to 6 months from their first dose of sotorasib, discontinuation of sotorasib plus 30 days, withdrawal of consent, death, or lost to follow-up, whichever occurs first. Investigators are requested to make every effort to enroll all patients in a total surveillance method during the enrollment period.

• Summary of Subject Eligibility Criteria

Inclusion Criteria

- subjects prescribed sotorasib in clinical practice according to the approved therapeutic indications, dosage, and administration in South Korea
- subjects or their authorized representative who provide written informed consent to participate in this study

Exclusion Criteria

- Subjects with contraindications as listed on the approved local label
- subjects concurrently participating in another interventional study will not be allowed to participate in this study
- subjects received any prior treatment with sotorasib before day 1 visit

• Follow-up

Subjects will be followed from their first dose of sotorasib through the completion of 6 months of sotorasib use, discontinuation of sotorasib plus 30 days, withdrawal of consent, death, or lost to follow-up, whichever occurs first.

Data will be collected from each enrolled subject's medical records.

- Variables
 - Outcome Variables
 - primary outcome measures: incidence of adverse events, serious adverse events, adverse drug reactions, serious adverse drug reactions, unexpected adverse events, unexpected serious adverse events, unexpected adverse drug reactions, unexpected serious adverse drug reactions, adverse events leading to sotorasib discontinuation, and fatal events
 - secondary outcome measure: ORR and clinical outcome measure by the Investigator

• Study Sample Size

Per the most recent MFDS regulatory requirements, the study intends to enroll all eligible subjects in South Korea during the 2 years enrollment period but not less than 25 subjects to collect safety and effectiveness information for the final analysis. Investigators at participating medical sites are requested to make every effort to enroll subjects in a total surveillance method during the enrollment period.

• Data Analysis

The data will be summarized descriptively.

The Safety Analysis Set will include all subjects who received at least 1 dose of sotorasib in accordance with the approved therapeutic indications, dosage, and administration in South Korea and completed at least 1 safety follow-up. The incidence of adverse events will be summarized to include all treatment-emergent adverse events recorded from the start of sotorasib on this study or any worsening of medical conditions initially experienced before initiation of this study. All adverse events will be graded using the most recent Common Terminology Criteria for Adverse Events (CTCAE) version. This summary for adverse events will be performed for the following categories:

- all adverse events and adverse drug reactions
- serious adverse events and serious adverse drug reactions
- unexpected adverse events and unexpected adverse drug reactions
- unexpected serious adverse events and unexpected serious adverse drug reactions
- adverse events leading to sotorasib discontinuation
- fatal events

The 6-month cumulative incidence of adverse events will be presented as frequency and percentage.

The Full Effectiveness Analysis Set will include all subjects from the Safety Analysis Set who also have at least 1 follow-up tumor assessment to estimate the ORR after initiation of sotorasib. In addition, the investigators should evaluate the clinical outcome of each subject during the surveillance period.

Subjects will be followed from their first dose of sotorasib through completion of 6 months of sotorasib use, discontinuation of sotorasib plus 30 days, withdrawal of consent, death, or lost to follow-up, whichever occurs first.

The study protocol does not define exact referral dates for follow-up visits.

Follow-up visits occur during routine practice. The investigator documents the date of initial visit and follow-up in the electronic case report form (eCRF) and follows the study procedures pertaining to data collection for the visit.

5. Amendments and Updates

None

6. Rationale and Background

6.1 Diseases and Therapeutic Area

Disease State/Therapeutic Area

Lung cancer is the leading cause of cancer death, with more than 80% of all lung cancer cases classified as NSCLC. In South Korea, lung cancer is the third most common cancer, with 28651 cases of lung cancer and 20505 deaths from lung cancer reported in 2020 (Global Cancer Observatory, 2021). Advanced NSCLC (stage IIIB/C and IV) is a serious and life-threatening disease, with a 5-year survival rate of 23.5% in South Korea (National Cancer Statistics, 2020).

Based on the estimated prevalence of the Kirsten rat sarcoma viral oncogene homolog DNA (*KRAS*) *KRAS* DNA with a mutation resulting in a G12C (*KRAS* p.G12C) mutation in NSCLC (approximately 2% to 4% in South Korea [Park et al, 2017; Shin et al, 2017; Sun et al, 2013]) and incidence of lung cancer (Korea National Cancer Information Center, 2020) it is estimated approximately 450 to 900 new patients in the South Korea are diagnosed with *KRAS* p.G12C-mutated NSCLC each year.

Treatment of advanced NSCLC has improved since the clinical practice use of immunotherapies (the checkpoint inhibitors) and targeted therapies for a variety of oncogenic mutations. No anticancer therapies are currently approved for the treatment of patients with NSCLC that specifically target tumors that have the *KRAS p.G12C* mutation (Román et al, 2018; McCormick, 2016).

Amgen Investigational Product Background: Sotorasib

Sotorasib is a small molecule that specifically and irreversibly inhibits the Kirsten rat sarcoma viral oncogene homolog protein (KRAS) with a G12C mutation (KRAS^{G12C}) mutant protein (Canon et al, 2019). Sotorasib binds to the P2 pocket of KRAS^{G12C} adjacent to the cysteine at position 12 and the nucleotide-binding pocket. The inhibitor contains a thiol-reactive portion that covalently modifies the cysteine residue and locks KRAS^{G12C} in an inactive, guanosine diphosphate-bound conformation. This blocks the interaction of KRAS^{G12C} with effectors such as RAF proto-oncogene

serine/threonine-protein kinase (RAF), thereby preventing downstream signaling, including the phosphorylation of extracellular signal regulated kinase (ERK) (Canon et al, 2019; Simanshu et al, 2017; Ostrem et al, 2013).

Sotorasib treatment impairs cell growth and induces apoptosis only in tumor cell lines and xenografts that have the *KRAS p.G12C* mutation (Canon et al, 2019). Blockade of KRAS^{G12C} signaling by sotorasib also enhances antigen presentation and inflammatory cytokine production in tumors to inflame the tumor microenvironment and drive permanent anti-tumor immunity.

In advanced NSCLC patients enrolled in the pivotal phase 2 portion of Study 20170543, the confirmed objective response rate is 37.1% (95% CI: 28.6, 46.2). The most common treatment-related adverse events (as determined by the investigator) included: diarrhea (31.0%), nausea (19.0%), increased alanine aminotransferase (15.1%), increased aspartate aminotransferase (15.1%), fatigue (11.1%), and vomiting (7.9%). Treatment-related adverse events led to treatment discontinuation in 7.1% of patients. All fatal adverse events were considered unrelated to sotorasib.

6.2 Rationale

In South Korea, it is mandatory to conduct active pharmacovigilance surveillance as a part of the RMP to investigate post-marketing safety and effectiveness in patients treated with newly approved drugs. To comply with this Korean MFDS regulation, Amgen Limited Korea will conduct a post-marketing surveillance study to evaluate the safety and effectiveness of sotorasib in routine clinical practice. Amgen seeks to enroll all eligible patients in South Korea during the 2-year enrollment period to collect safety and effectiveness information for the final analysis. In addition to meeting the MFDS regulatory requirements, this study also will provide additional safety and effectiveness data beyond that generated in the registrational sotorasib study (Study 20170543).

6.3 Feasibility and Futility Considerations

Not applicable.

6.4 Statistical Inference (Estimation or Hypothesis)

No hypothesis will be tested. Instead, the proposed study will provide descriptive data on use of sotorasib and subject characteristics in the post-marketing setting in South Korea; the incidence of adverse events, serious adverse events, adverse drug reactions, serious adverse drug reactions, unexpected adverse events, unexpected serious adverse events, unexpected adverse drug reactions, unexpected serious reactions, adverse events leading to sotorasib discontinuation, and fatal events; ORR after initiation of sotorasib.

7. Research Question and Objectives

According to local regulation, a post-marketing surveillance study is required for orphan drugs newly approved in South Korea to collect safety and effectiveness data in routine clinical practice. An observational multicenter study design is chosen to meet the local regulations in South Korea.

7.1 Primary

The primary objective of this study is to describe the safety of sotorasib in post-marketing clinical practice within the approved indication by estimating the incidence of adverse events, serious adverse events, adverse drug reactions, serious adverse drug reactions, unexpected adverse events, unexpected serious adverse events, unexpected adverse drug reactions, unexpected serious adverse drug reactions, adverse events leading to sotorasib discontinuation, and fatal events among subjects receiving sotorasib within the approved indication in the post-marketing setting in South Korea as required by the MFDS.

7.2 Secondary

The secondary objective of this study is to describe effectiveness of sotorasib in clinical practice within the approved indication by estimating the ORR and clinical outcome measure by the Investigator.

8. Research Methods

8.1 Study Design

This is an observational multicenter prospective cohort study in subjects who are prescribed sotorasib within the approved indication in a post-marketing setting in South Korea.

Subjects that meet the eligibility criteria (Section 8.2.3) and sign the informed consent will be enrolled. Subjects will be seen by their physician per local standard of care and should receive sotorasib in accordance with the approved therapeutic indication, dosage, and administration in South Korea. Adverse events, serious adverse events, adverse drug reactions, serious adverse drug reactions, adverse events leading to discontinuation of sotorasib, fatal events, other safety findings and spontaneously reported product complaints will be collected for each subject from their first dose of sotorasib on day 1 through the end of study (EOS). Treatment responses will be

collected after day 1 through EOS. Six-month cumulative subject incidence of adverse events will be reported and summarized. Unexpected adverse events, unexpected serious adverse events, unexpected adverse drug reactions, and unexpected serious adverse drug reactions will be analyzed from the collected adverse events/serious adverse events/adverse drug reactions/serious adverse drug reactions as part of a special analysis. Overall response rate is defined as the proportion of patients with a Best Overall Response (BOR) of confirmed complete response (CR) or confirmed partial response (PR) and will also be reported and summarized. The investigators should evaluate the clinical outcome of each subject during the surveillance period and assign one of the following descriptions: improved, not changed, disease progression, or unable to evaluate. End of study is defined as completing 6 months of sotorasib use, discontinuation of sotorasib plus 30 days, withdrawal of consent, death, or lost to follow-up, whichever occurs first. All data collected for the purpose of this study will be entered into the eCRF.

For a full list of data elements, including the timing for each data abstraction, please refer to the schedule of data collection in Table 1.

Table 1. Schedule of Data Collection

			Visit(s) Following Day 1
	Baseline Eligibility Periodª	Start of Sotorasib Day 1ª	Data will be collected from medical records at each subsequent site visit (expected to occur at ~ day 21, month 2, month 4, and month 6) through EOS
GENERAL ASSESSMENTS			
Eligibility Review	Х	Х	
Informed Consent	Х	X completed before and up to day 1	
DATA COLLECTED (If available in Medical Records)			
Physical measurements height weight 	х		
Demographic and smoking status data • age • sex • smoking history	х		
allergic historypregnancy and lactation status			
Clinical and tumor characteristics • date of initial diagnosis • clinical stage • histology	x		
 comorbidities, including hepatic impairment and renal impairment ECOG performance score 			Page 1 of

Footnotes defined on last page of the table

Table 1. Schedule of Data Collection

			Visit(s) Following Day 1
	Baseline Eligibility Periodª	Start of sotorasib Day 1ª	Data will be collected from the medical records at each subsequent site visit (expected to occur at ~ day 21, month 2, month 4, and month 6) through EOS
DATA COLLECTED (If available in Medical Records)			
Treatment history	Х		
 prior systemic treatment received in the advanced disease setting 			
 dose, unit and frequency, start and stop dates 			
Prior and concomitant medications	Х		Х
 record history from 1 year before first dose on day 1 through the end of study 			
 dose, unit and frequency, start and stop dates 			
Safety events collection*		Х	Х
adverse events			Safety events will be entered in the
• serious adverse events			eCRF as data become available
 adverse drug reactions 			Safety events recorded in medical records from the time of first dose on day 1 through EOS will be collected
 serious adverse drug reactions 			
 adverse events leading to sotorasib discontinuation 			
fatal events			
 other safety findings 			
 spontaneously reported product complaints 			
Effectiveness collection			Xp
 ORR based on real-world RECIST assessment using RECIST criteria v1.1 or later 			
 clinical outcome measure by the Investigator 			

Table 1. Schedule of Data Collection

			Visit(s) Following Day 1
	Baseline Eligibility Periodª	Start of sotorasib Day 1ª	Data will be collected from the medical records at each subsequent site visit (expected to occur at ~ day 21, month 2, month 4, and month 6) through EOS
DATA COLLECTED (If available in Medical Records)			
Treatment with sotorasib		Х	X
 indication 			
• dose			
start date			
• end date			
 frequency of sotorasib administration, drug withdrawal of sotorasib any time from initiation of sotorasib treatment 			
			Page 3 of 3

ECOG = Eastern Cooperative Oncology Group; eCRF = electronic case report form; ORR = overall response rate; RECIST = response evaluation criteria in solid tumors

Safety events*: Unexpected adverse events, unexpected serious adverse events, unexpected adverse drug reactions, and unexpected serious adverse drug reactions will be analyzed from the collected adverse events/serious adverse events/adverse drug reactions/serious adverse drug reactions as part of a special analysis.

^a Baseline and day 1 assessments can occur on the same day.

^b Tumor assessment will not be completed at Day 21

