8.3.3 Covariate Assessment

- demographics, physical measurements, and smoking status (age, sex, height, weight, smoking history, allergic history, pregnancy, or lactation status)
- clinical and tumor characteristics (date of initial diagnosis, clinical stage, histology, comorbidities [including hepatic impairment and renal impairment], Eastern Cooperative Oncology Group [ECOG] performance score)
- prior systemic treatment received in the advanced disease setting (please refer to the table of data collection)
- sotorasib treatment (please refer to the table of data collection)
- prior and concomitant medications (please refer to the table of data collection)
- adverse events, serious adverse events, adverse drug reactions, serious adverse drug reactions, unexpected adverse events, unexpected serious adverse events, unexpected adverse drug reactions, unexpected serious adverse drug reactions, adverse events leading to sotorasib discontinuation, fatal events, other safety findings, spontaneously reported product complaints.
- treatment response: ORR based on RECIST criteria v1.1, evaluation of investigator (improved, not changed, disease progression, unable to evaluate)

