8.7.1.2 Final Analysis

The final analysis will be conducted when the last enrolled subject reaches the EOS. A snapshot of the finalized database will be used for analysis. All analyses will be performed using SAS[®] 9.4 or later versions. Safety and effectiveness data collected at scheduled time points will be used for analysis.

The Safety Analysis Set will include all subjects who received at least 1 dose of sotorasib in accordance with the approved therapeutic indications, dosage, and administration in South Korea and completed at least 1 safety follow-up. The safety analysis will be the analysis conducted using the Safety Analysis Set, and will describe the following assessments:

- adverse events
- serious adverse events
- adverse drug reactions
- serious adverse drug reactions
- unexpected adverse events
- unexpected serious adverse events
- unexpected adverse drug reactions
- unexpected serious adverse drug reactions
- adverse events leading to sotorasib discontinuation
- fatal events

The Full Analysis Set (ie, Effectiveness Analysis Set) will include all subjects from the Safety Analysis Set who have at least 1 follow-up tumor assessment to estimate the ORR after initiation of sotorasib. Subjects will be followed from their first dose of sotorasib through the completion of 6 months of sotorasib use, discontinuation of sotorasib plus 30 days, withdrawal of consent, death, or lost to follow-up, whichever occurs first. In addition, investigators should evaluate the clinical outcome of each subject during the surveillance period and assign one of the following descriptions:

- improved
- not changed
- disease progression
- unable to evaluate

The data of subjects used outside of the approved indication will be analyzed separately.

The study protocol does not define exact referral dates for follow-up visits.

Follow-up visits occur during routine practice. The investigator documents the date of initial visit and follow-up in the eCRF and follows the study procedures pertaining to data collection for the visit.

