8.7.2 Planned Method of Analysis

8.7.2.1 General Considerations

The statistical analysis in this post-marketing study will be descriptive in nature, and no hypothesis testing will be performed. Categorical outcomes will be summarized by the number and percentage of subjects in each category. Continuous outcomes will be summarized by the number of non-missing values, mean, standard deviation, median, lower and upper quartiles, and minimum and maximum values. Subject incidence will be summarized for adverse events, serious adverse events, adverse drug reactions,

serious adverse drug reactions, unexpected adverse events, unexpected serious adverse events, unexpected adverse drug reactions, unexpected serious adverse drug reactions. Also, 95% CI will be presented based on exact method for incidence. ORR will be reported with a Clopper-Pearson exact confidence interval.

Difference in safety or effectiveness results by subject's background factor can be analyzed by Chi-square test and to estimate factors that may affect the safety or effectiveness results, multivariate analysis can be conducted.

Additional information will be collected according to the RMP when adverse events related to the Important Safety Specification Requiring Further Evaluation Items in RMP are collected. The special investigation group (elderly, children, hepatic impairment, renal impairment, pregnancy, or lactation) will be analyzed separately.

All adverse events are tabulated in the report using the latest version of Medical Dictionary for Regulatory Activities (MedDRA), using System Organ Class (SOC) and Preferred Term (PT).

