8.7.2.4.2 Analysis of Secondary Endpoint

Effectiveness Analysis: Investigators will use the RECIST criteria v1.1, or a more recent version if available, to assess the tumors based on magnetic resonance imaging or computed tomography scans beginning at the baseline and succeeding visits as part of routine clinical practice. Based on all the available data and for each time point post-baseline, the site investigator will classify the tumors into one of the categories: CR, PR, SD, PD or NE. The number and percentage of subjects with a BOR of CR, PR, SD, and PD will be presented. The ORR (%) across all timepoints = ([Number of BOR of confirmed CR + Number of BOR of confirmed PR]/Total number treated) x 100. In addition, investigators should evaluate the clinical outcome of each subject during the surveillance period and assign one of the following descriptions:

- improved
- not changed
- disease progression
- unable to evaluate

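### The investigator's clinical-outcome scale has no label for worsening or death without disease progression, so its planned percentages can be distorted

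*Protocol*

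**What the plan says.** Protocol Section 7.2 sets the secondary objective as "estimating the ORR and clinical outcome measure by the Investigator", so the investigator's rating is one of two effectiveness measures.

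Section 8.1 has the investigator "assign one of the following descriptions: improved, not changed, disease progression, or unable to evaluate". The same four labels recur in Sections 8.3.2, 8.7.1.2 and 8.7.2.4.2, and in Section 8.3.3 as "evaluation of investigator (improved, not changed, disease progression, unable to evaluate)". No section gives criteria for the labels, fixes when within the surveillance period the rating is made, or says how to label a subject who deteriorates or dies without progression.

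On analysis, Section 8.7.2.1 states that "Categorical outcomes will be summarized by the number and percentage of subjects in each category" and that "no hypothesis testing will be performed". No denominator is given for this measure. Section 8.7.1.2 describes it in the same paragraph as the effectiveness set, which is limited to Safety Analysis Set subjects "who have at least 1 follow-up tumor assessment to estimate the ORR after initiation of sotorasib". A footnote to Table 1 says there is no tumour assessment at Day 21, and the next expected visit is around month 2.

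**The concern.** *Improved* and *not changed* read as clinical judgements, but the only negative label names a disease event. A subject who declines with a stable tumour, or who dies of another cause before progression is documented, has no label that describes what happened. The investigator must still choose one.

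Two things are at stake. First, *not changed* and *unable to evaluate* can contain failures, and the mix can depend on site habit. Second, the code list goes into the eCRF, so a distinction not collected there cannot readily be recovered at analysis. Table 1 schedules ECOG score and weight at baseline only, so no repeated functional measure can stand in.

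The unstated denominator adds a separate problem. If the effectiveness set is used, subjects who leave before a first scan disappear from a measure that needs no scan.

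**Working it through.** The protocol states no expected rate or precision for this measure, so there is no figure to reproduce. The check is direct proportions.

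**Inputs**
- N = 25, the minimum number of subjects (Section 8.5).
- Assumed for illustration: 9 subjects improved and 9 truly not changed. The other 25 − 9 − 9 = 7 are failures, and nobody is truly unevaluable.
- Of those 7, d worsen or die without progression. The protocol gives no value for d, so d = 1, 2, 3 and 5 are shown.

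**Step 1: planned percentages over all subjects.** Each misplaced subject moves a category by 1/25 = 4 points. The d subjects add d/25 to *not changed* or *unable to evaluate*. *Disease progression* is reported as (7 − d)/25, while true failures are 7/25 = 28%. *Improved* is 9/25 throughout.

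**Step 2: the d subjects leave the denominator,** as happens if they have no follow-up scan and the effectiveness set is used. *Improved* becomes 9/(25 − d).

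| d | Added to *not changed* or *unable to evaluate* | *Disease progression* reported (true failures 28%) | *Improved*, all subjects | *Improved*, d subjects dropped |
|---|---|---|---|---|
| 1 | 4 points | 6/25 = 24% | 36.0% | 9/24 = 37.5% |
| 2 | 8 points | 5/25 = 20% | 36.0% | 9/23 = 39.1% |
| 3 | 12 points | 4/25 = 16% | 36.0% | 9/22 = 40.9% |
| 5 | 20 points | 2/25 = 8% | 36.0% | 9/20 = 45.0% |

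**Step 3: a pooled rate, which the protocol does not plan.** *Improved* plus *not changed* should be 18/25 = 72%. If the d subjects are labelled *not changed*, it becomes (18 + d)/25 = 76%, 80%, 84% and 92%. If they are labelled *unable to evaluate* and then excluded, it becomes 18/(25 − d) = 75.0%, 78.3%, 81.8% and 90.0%.

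**Reading the steps together.** The negative and neutral shares can shift under the analysis as planned. *Improved* shifts only if subjects leave the denominator. That can happen through the effectiveness set: follow-up ends at death or 30 days after stopping, so a subject who dies early, or stops within roughly the first month, can reach end of study before the month 2 assessment.

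**The case against.** A reader might infer that the secondary endpoint is biased upward. The documents do not support that as a statement of fact. Only per-category percentages are planned. No success rate is defined, no pooling of labels is stated, and nothing says *unable to evaluate* is removed. Over all subjects, *improved* stays at 36.0% in the example for every d. ORR has its own formula, "Number of BOR of confirmed CR + Number of BOR of confirmed PR]/Total number treated", and does not use this scale.

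It is also tempting to size the problem from Section 6.1: "Treatment-related adverse events led to treatment discontinuation in 7.1% of patients". That figure counts stopping for toxicity, not clinical worsening; a subject who stops may be stable or responding. The protocol gives no rate of worsening or death without progression, and none should be implied.

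Other points on that side are fair:
- No section says such subjects are labelled *not changed* or *unable to evaluate*. The scale is not tied to RECIST, so an investigator might use *disease progression* for clinical decline.
- *Unable to evaluate* is a residual label, so every subject can be given something.
- Fatal events and adverse events leading to discontinuation are primary safety endpoints, and worsening of an underlying condition counts as an adverse event (Section 10.1.1). These cases therefore reach the report.
- Keeping toxicity and unrelated deaths out of an effectiveness label is a defensible choice.
- Labelling rules may sit in the eCRF instructions mentioned in Section 8.3.4, which are not shown.

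These points remove the claim of a demonstrated bias. They do not remove the gap. Several admissible labels for the same subject mean the shares can depend on the site, a residual label that also holds known failures is hard to interpret, and nothing links the safety tables to this measure. If leaving such cases out is intended, the protocol should say so.

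**Conclusion.** The point holds in limited form. The scale has no label or rule for worsening or death without progression, so the planned shares of *not changed* and *unable to evaluate* can be distorted by 4 points per subject at N = 25, and the one negative category can understate failures. Each subject counts for less if enrolment exceeds the minimum.

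Inflation of *improved* is conditional: it requires the effectiveness set as denominator and excluded subjects who did not improve. The move from 36.0% to 39.1% assumes 9 improved subjects and the loss of 2 of 25; it is not an estimate for this study.

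Severity is minor. The study is descriptive, no decision rule depends on this scale, and deaths are reported elsewhere. Classification: cheap improvement.

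**What to change.** In Sections 8.1, 8.3.2, 8.3.3, 8.7.1.2 and 8.7.2.4.2, and in the eCRF, replace *disease progression* with *worsened* and record a reason: disease progression, other clinical deterioration, or death. The progression count stays available from the reason, and unrelated deaths can be shown separately. Stopping for toxicity should not by itself imply *worsened*.

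State that all four labels are tabulated over every subject in the Safety Analysis Set, with *unable to evaluate* kept in the denominator and no follow-up scan required.

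The cost is one code-list change with matching protocol wording, and no extra visit or procedure. It is best made before data entry, because later recoding means going back to the charts. The distribution reported may look less favourable.
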